Appendix 16: End of Study Participant Preference Survey (Sample)

| Participant Number: | | | | | |
|--|--|--|--|--|--|
| | | | | | |
| Thank you for participating in this study. Now that you have experienced the use of two urine collection devices, please answer a few questions about your experiences with the devices. | | | | | |
| As a reminder, during the study, you used two devices overnight while sleeping: | | | | | |
| During the first part of the study, you used the PureWick™ Urine Collection System/Hollister Female Urinary Pouch External Collection Device. | | | | | |
| During the second part of the study, you used th System/Hollister Female Urinary Pouch Extern | ne PureWick™ Urine Collection al Collection Device. | | | | |

1. Do you remember using each of these devices?

Yes No

<*If No or if there is significant difficulty in differentiating the 2 study phases, discontinue the interview.*>

2. Which device did you prefer?

PureWick[™] Urine Collection System

Hollister® Female Urinary Pouch External Collection Device

3. What made you choose the <PureWick/Hollister> device? Why did you prefer that device?

<*Ask follow-up questions, as much as practical, to better understand the participant's preference>*

- 4. Please think about how your skin felt when using each device. Which caused you to feel LESS skin irritation, the PureWick[™] device or Hollister[®] device?
 - PureWick[™] Urine Collection System
- Hollister® Female Urinary Pouch External Collection Device
- No difference
- _____ Do not recall

Why did you choose the PureWick/Hollister?

Thank you for taking the time to answer these questions!

1.0 INTRODUCTION

1.1 Background and Rationale

The PureWick[™]® Female External Catheter (PureWick[™] FEC) is an external drainage device to address the need for an effective, non-invasive method of managing urine output in adult incontinent women. The device utilizes suction to drain urine away from the patient through tubing that is connected to a collection canister. PureWick[™] FEC can use either wall suction (acute care setting) or a free-standing PureWick[™] FEC is a Class I, 510(k) exempt device. In Europe, the PureWick[™] FEC is a Class I, CE marked, non-sterile device.

The study will collect clinical and quality of life data from patients requiring urine output management overnight in the home setting, which will aid reimbursement in France and the United States (U.S.). This pilot will inform the sample size and the frequency of nursing visits for the future home-setting, randomized control trial.

1.2 Objectives and Endpoints

Objectives and Endpoints	Objective(s)	Endpoint(s)
	Primary	Primary
	To compare efficacy and safety of PureWick™ System and Hollister⊚ Female Urinary Pouch External Collection	 Efficacy – Daily capture rate via bed pad weights and captured volume.
	Device	 Safety – Daily skin irritation score using the Draize Scale

Table 1. Objectives and Endpoints

Study ID: UCC-8007

Version No:

01

Secondary	Secondary
 To assess impact of PureWick™ System and Hollister® Female Urinary Pouch External Collection Device on Nocturnal Incontinence related Quality of Life and sleep disturbance. 	 Nocturia Quality of Life (N-QOL) score collected at baseline and every 2 weeks during treatment PROMIS Sleep Disturbance questionnaire at baseline and every 7th days during treatment.
 Tolerability – To assess the tolerance of PureWick[™] System and Hollister® Female Urinary Pouch External Collection Device over the expected duration of use 	 Tolerability – Number of days of actual use of both devices & Discontinuation rate attributed to the device's inconvenience or discomfort
 To assess participant comfort and ease of use of PureWick™ System and Hollister® Female Urinary Pouch External Collection Device 	• Overall comfort and ease of use scores on a 5-point Likert scale (brief questionnaire) collected at the end of each treatment phase
 To assess participant final preference between the PureWick™ System and Hollister® Female Urinary Pouch External Collection Device after treatment completion 	• Conduct end of study interview. Asking for details of participant's use preference of both devices during treatment phase.

Acceptance Criteria and/or Investigation Hypothesis
 None. No formal hypothesis test is planned for this pilot study.

Statistical Analysis Plan	Page No. 5 of 20
Study ID: UCC-8007	Version No: 01

2.0 STUDY DESIGN

2.1 Study Design

This is a prospective, open-label, 2 by 2, crossover trial to evaluate the safety, efficacy, and patient quality of life of PureWick[™] System in comparison with Hollister® Female Urinary Pouch. Participants are randomized 1:1 to use PureWick[™] System in phase 1 and Hollister® Female External Pouch in phase 2, or to use Hollister® Female Urinary Pouch in phase 1 and PureWick[™] System in phase 2. Each phase lasts 4 weeks, with a 2-4 week washout period between phase 1 and phase 2. Capture rates and Draize Scale are assessed daily during both phases. Nocturia-Quality of life is assessed at baseline and every 14 days during phases 1 and 2. PROMIS Sleep disturbance is assessed at baseline and every 7 days during phases 1 and 2. User preference questionnaires are completed at the completion of each treatment phase with final user preference between the PureWick[™] System and Hollister® Female Urinary Pouch External Collection Device after completion of both treatments. The primary efficacy endpoint is the mean of daily capture rate. The primary safety endpoint is the mean of daily assessments of Draize Scale.

2.2 Study Population

Adult female participants requiring urine output management overnight in the home setting will be recruited for this study by the study site from their current patient list. Study sites may advertise and recruit new patients if eligible participants from the patient list have been exhausted.

To best mimic potential users of the PureWick[™] System, participants >18 years of age will be enrolled. It is desired that at approximately 90% of participants are >65 years of age. This study will enroll approximately 30 participants.

2.2.1 Inclusion Criteria

In order to be eligible to participate in this study, an individual must meet all of the following criteria:

- 1. Adult Female Participants >18 years of age at the time of signing the informed consent.
- Currently use diapers or equivalent at night for urine capture ("Change complet" (FR))
- 3. Willing to comply with all study procedures in this protocol
- 4. Provision of signed and dated informed consent form

2.2.2 Exclusion Criteria

Participants are excluded from the study if any of the following criteria apply:

- 1. Has frequent episodes of bowel incontinence without a fecal management system in place; or
- 2. Has moderate to heavy menstruation and cannot use a tampon or menstrual cup; or
- 3. Has Urinary tract, vaginal or other chronic infections, active genital herpes; or
- 4. Has Urinary retention; or
- 5. Is agitated, combative, and/or uncooperative and may remove the external catheter or pouch; or
- 6. Has any wound, open lesion or irritation on the genitalia, perineum, or sacrum; or
- 7. Has any pre-existing neurological, psychiatric, or other condition that would

confound quality of life assessment or would make it difficult to self-report on quality-of-life questionnaires in the opinion of the investigator; or

- 8. Is known to be pregnant at time of enrollment (for women of childbearing age); or
- 9. Any other condition that, in the opinion of the investigator, would preclude them from participating in the study.

2.3 Randomization and Blinding

Subjects will be randomized 1:1 to the two sequences of treatment (using PureWick[™] FECs in phase 1 and Hollister® Female External Pouch in phase 2, or the reversed order). This design allows the evaluation of elements such as the carryover effect, period effect, and sequence effect. To begin treatment phase in either the U.S. or France, using a prepared randomization schedule participants will be randomized 1:1 to use either PureWick[™] FEC in phase 1 and Hollister® FUP in phase 2, or vice versa. Block randomization will be carried out using a fixed block size of 2 and stratified by investigational site and geography.

This is an open-label study. Blinding is not applicable.

2.4 Sample Size

Approximately 30 participants will be enrolled. The sample size is planned based on operational and practical considerations and is adequate for the purpose of this pilot study.

2.5 Interim Analysis

Not applicable.

2.6 Study Procedure

Table 2. Schedule of Activities

RD	Statistical Analysis Plan	Page No. 7 of 20
	Study ID: UCC-8007	Version No: 01

			Daily Study Home Visits											
Procedure	Screening / Enrollment	Ph 1 Baseline Day 1	Ph1 Day 2-14	Ph1 Day 15	Ph1 Day 16-28	Ph1 Day 29	Ph1 Day 30	Wash out Day 29- 42 (+14 days)	Ph2 Baseline Day 1	Ph2 Day 2-14	Ph2 Day 15	Ph2 Day 16-28	Ph2 Day 29	Ph2 Day 30
Informed consent	Х													
Inclusion and exclusion criteria	Х													
Demography	Х													
Medical history	Х													
Katz ADL Index	Х													
Participant ID Assignment and Randomization	Х													
Introduction to Home Nurses (On site or Virtual)	Х													
Visual Skin Assessment & Draize Scoring (Both site and Nurses)		Х	Х	х	Х	Х	Х		Х	Х	Х	Х	Х	Х
Nurses Confirm Study Supplies		Х							Х					

Statistical Analysis Plan	Page No. 8 of 20
Study ID: UCC-8007	Version No: 01

		Daily Study Home Visits												
Procedure	Screening / Enrollment	Ph 1 Baseline Day 1	Ph1 Day 2-14	Ph1 Day 15	Ph1 Day 16-28	Ph1 Day 29	Ph1 Day 30	Wash out Day 29- 42 (+14 days)	Ph2 Baseline Day 1	Ph2 Day 2-14	Ph2 Day 15	Ph2 Day 16-28	Ph2 Day 29	Ph2 Day 30
Nurses Have Participant Complete N-QOL		х		X*		X*			х		X*		X*	
Nurses Have Participant Complete PROMIS Sleep Disturbance		x	X* Day 8	X* Day 15	X* Day 22	X* Day 29			x	X* Day 8	X* Day 15	X* Day 22	X* Day 29	
Nurses Conduct Device Training w/Participants		Х							Х					
Nurses Pre-weigh urine canister or graduated cylinder		Х							Х					
Nurses Pre-Weigh Overnight Pads and Mesh underwear (if applicable)		Х	X	X	X				Х	X	X	X		
Participants wear investigational device		Х	х	х	Х				Х	Х	Х	х		

BD	Statistical Analysis Plan	Page No. 9 of 20
	Study ID: UCC-8007	Version No: 01

			Daily Study Home Visits											
Procedure	Screening / Enrollment	Ph 1 Baseline Day 1	Ph1 Day 2-14	Ph1 Day 15	Ph1 Day 16-28	Ph1 Day 29	Ph1 Day 30	Wash out Day 29- 42 (+14 days)	Ph2 Baseline Day 1	Ph2 Day 2-14	Ph2 Day 15	Ph2 Day 16-28	Ph2 Day 29	Ph2 Day 30
Nurses Measure Urine Output			Х	Х	Х	Х				Х	Х	Х	Х	
Nurses Post-Weigh Overnight Pads and Mesh Underwear (if applicable)			X	X	х	X				X	X	X	Х	
Participant Completes Preference and Ease of Use Survey*						X*							X*	
Participant Completes End of Study Preference Survey														Х*
AE review (If applicable)		J										l		⇒
SAE review (If applicable)														\Rightarrow
Device Deficiencies (If applicable)		Ţ												

Statistical Analysis Plan	Page No. 10 of 20
Study ID: UCC-8007	Version No: 01

*To be completed per treatment schedule or upon treatment discontinuation, whichever comes first.

3.0 INTENDED STATISTICAL SOFTWARE AND DATA INFORMATION

3.1 Intended Statistical Software

SAS Version 9.4 (SAS Institute, Cary, NC) or above will be used to perform analyses and generate outputs.

3.2 Data Information

Analysis datasets and a document outlining the specification of analysis datasets will be stored in a version-controlled environment.

4.0 ANALYSIS POPULATION SET(S)

4.1 Populations Definitions

The following populations are defined:

Population	Description	
Enrolled	Subjects who signed ICF.	
Intent-to-Treat (ITT)	Subjects who signed ICF and randomized to a treatment sequence.	
As-Treated (AT)	ITT subjects, grouped by actual treatment sequence, if different from planned treatment sequence.	
Per-Protocol (PP)	ITT subjects without major protocol deviation.	

ITT population will be used for the analyses of endpoints. Sensitivity analyses may be carried out using AT or PP population.

Study ID: UCC-8007

Version No:

01

GFM-10082C

5.0 STATISTICAL ANALYSIS / CALCULATIONS

5.1 Derived Variables

Daily capture rate (%) is defined as: captured urine weight / (captured urine weight + leaked urine weight) *100, where

- Captured urine weight is defined as:
 - PureWick(TM): Canister final weight (g) Canister starting weight (g), and
 - Hollister(R): Graduated cylinder final weight (g) Graduated cylinder baseline weight (g)
- Leaked urine weight is defined as:
 - bed pad 1 post-use weight (g) bed pad 1 pre-use weight (g) when the answer for "Was 2nd bed pad used?" is equal to "No" on Case Report Form (CRF) page PureWick(TM) Participant Placement or Hollister(R) Female External Collection Pouch Participant Placement and OR
 - (pad 1 post-use weight (g) bed pad 1 pre-use weight (g)) +(pad 2 post-use weight (g) bed pad 2 pre-use weight (g)) when the answer for "Was 2nd bed pad used?" is equal to "Yes" on Case Report Form (CRF) page PureWick(TM) Participant Placement or Hollister(R) Female External Collection Pouch Participant Placement
 - OR
 - (pad 1 post-use weight (g) bed pad 1 pre-use weight (g)) +(pad 2 post-use weight (g) bed pad 2 pre-use weight (g)) +(Mesh underwear post-use weight (g) Mesh underwear pre-use weight (g) when theDaily answer for "Was 2nd bed pad used?" is equal to "Yes" and when the answer for "Did participant use the mesh underwear provided while using the study device?" is equal to "Yes"(This scenario only applies to PureWick™ group.).
 - o OR
 - (pad 1 post-use weight (g) bed pad 1 pre-use weight (g)) +(Mesh underwear post-use weight (g) Mesh underwear pre-use weight (g) when the answer for "Was 2nd bed pad used?" is equal to "No" and when the answer for "Did participant use the mesh underwear provided while using the study device?" is equal to "Yes" (This scenario only applies to PureWick™ group.).

A void of which (captured urine weight + leaked urine weight) < 10 g is considered not evaluable for the purpose of analyzing capture rate.

- 5.2 Analysis Methods
 - 5.2.1 General Considerations
 - 5.2.1.1 Handling of Missing Data

Endpoint data may be missing due to reasons including lost to follow-up or withdrawal of consent. For the primary efficacy endpoint, if capture rate assessments are missing for part of a treatment phase, derivation of the primary efficacy endpoint will be based on available data. For the primary safety endpoint, the main analysis will be based on available data. Sensitivity analyses may be performed for the primary safety endpoint where missing data is imputed using methods including linear interpolation or last-observation-carry-forward.

5.2.1.2 Poolability of Data

The effect of investigational site will be evaluated using regression models, with primary endpoint as the dependent variable, and treatment, investigational site, and the interaction term between treatment and investigational site as fixed effects.

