| Intervention(s)/Procedure(s) | The PI or designee/nurse defined by the Draize Skin Score will assess skin and determine readiness for each treatment phase. Participants assigned to both treatment arms will place and remove the FEC (female external catheter) or FUP (Female Urinary Pouch) after standardized teaching is completed on the first day of the treatment phase. Participants will use the device assigned in treatment phase 1 and 2 overnight while sleeping for 4 weeks (28 days). There will be a minimum washout period of 2 weeks (not to exceed 4 weeks) between treatment phases. | | | | |
| Investigational Sites | Approximately 2 sites in France and approximately 2 sites in the U.S. | | | | |
| Data Monitoring Committee | N/A | | | | |
| Regulatory Status | Post-Market, Non-significant risk PureWick[™] System Class I, non-sterile device, CE marked, currently marketed in Europe Class I, 510(k) exempt device currently marketed in the U.S. This investigation will use the PureWick[™] System for its intended purpose. | | | | |
| Trial Duration | Estimated start date: (First Patient In): 19 Sep 2023 Estimated end date (Final Clinical Study Report): October 2024 | | | | |

| Protocol Title | A Comparative Crossover Study on the Safety, Efficacy, and Patient Quality of Life Comparing PureWick TM System with an Established Comparator Overnight in the Home Setting for Incontinence. |
|------------------------------|--|
| Regulatory Agency Identifier | NCT05710718 (USA) |
| Number(s): | IDRCB: 2023-A01727-38 (France) |

CONFIDENTIAL

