4.0 STUDY DESIGN

4.1 Overall Design

In this prospective, post-market, multi-site, open-label, crossover trial, women with urinary incontinence requiring the use of diapers (changes complets (Fr)) at night will be 1:1 randomized to a treatment sequence using two devices (PureWick[™] System and Hollister® Female Urinary Pouch External Collection Device) and followed for approximately 10 weeks through 2 treatment phases.

Approximately 30 female participants from 2 sites will be enrolled into the study. Those meeting eligibility criteria will be treated according to the treatment sequence assigned during randomization. Participants will be trained by the nurses for the applicable product at the beginning of each treatment phase and have access to the IFU to review during each treatment phase. The total expected duration of subject participation is approximately 10 weeks. Participants will use the device assigned in treatment phase 1 overnight while sleeping for 4 weeks (28 days) before transitioning to the second assigned device in treatment phase 2. There will be a minimum washout period of 2 weeks (not to exceed 4 weeks) between treatment phases and a re-screening of eligibility criteria before the second phase. Participants assigned to both treatment arms will place and remove the FEC (female external catheter) or FUP (Female Urinary Pouch) after standardized teaching is completed on the first day of the treatment phase.

The primary objectives are to evaluate safety (skin injury) and efficacy (capture rate). Safety will be assessed using the Draize Scale and efficacy will be measured based on daily urine capture rate. Nurses will visit participants' homes daily to perform a skin assessment and collect urine measurements during the treatment phases. Participants will be withdrawn from the treatment phase if grade 4 is achieved in any category on the Draize skin irritation scale.

The secondary objectives are to assess quality of life, tolerability, preference, comfort and ease of use. Quality of life will be measured using self-reported changes in quality of life via the validated Nocturia Quality of Life (N-QOL) and PROMIS Sleep Disturbance assessments. Preference, comfort and ease of use will be measured using subjective evaluations of the therapy via participant surveys. Tolerability will be measured by number of days of actual use of both devices, and discontinuation rate attributed to the device's discomfort or inconvenience.

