10.4.2 Poolability of Data

The effect of investigational site will be evaluated using regression models, with primary endpoint as the dependent variable, and treatment, investigational site, and the interaction term between treatment and investigational site as fixed effects.

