10.6 Secondary Endpoint(s)

10.6.1 Questionnaire Nocturia Quality of Life (N-QoL)

The questionnaire consists of 13 items with a total score ranging from 0 to 52 higher score indicating greater impact of nocturia on quality of life). Descriptive statistics will be provided by treatment and by visit. Mixed effect linear regression model may be used, with treatment and sequence as the fixed effect, and participant as the random effect.

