5.2.2 Primary Endpoint

5.2.2.1 Primary Efficacy Endpoint

Capture rates is evaluated daily during participant phase 1 and phase 2. Daily capture rate (%) is defined as:

captured urine weight / (captured urine weight + leaked urine weight) *100

The primary efficacy endpoint is derived by computing the mean of daily capture rate during each phase. Descriptive statistics of the primary efficacy endpoint, including mean, standard deviation, median, and range will be provided by treatment and phase. A scatter plot for Capture Rate (y axis) vs. Day # (x axis), with different colors representing PureWick and Hollister and different panels representing study subject will also be provided. The summary statistics (mean, 95% CI for mean, median) for paired difference in mean daily capture rate between the two treatment arms and p-value from Wilcoxon signed rank test or Paired t-test will be provided. Normality test will be performed before the test, if the data is normally distributed then Paired t-test will be used, otherwise Wilcoxon signed rank test will be used. Sensitivity analyses using linear mixed model (with treatment, phase, and study day as the fixed effect, and participant as the random effect), beta regression (with treatment, phase, and study day as the fixed effect, and participant as the random effect) will also be performed.

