The questionnaire will be completed on Day 1, Day 15 and Day 29 of both study phases. We will categorize the questionnaire timepoint as baseline, week 1-2 (day 2-17) and week 3-4 (> day 17), respectively. If day 15 is missing, the latest record between day 2 and 17 will be used for week 1-2; if day 29 is missing, the latest record after day 17 will be used for week 3-4. Descriptive statistics will be provided by each questionnaire timepoint, treatment, and phase. A scatter plot for N-QoL (y axis) vs. Day # (x axis), with different colors representing PureWick and Hollister and different panels representing study subject will also be provided. Linear mixed model may be used, with treatment, phase, and day number as the fixed effect, and participant as the random effect.

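### The site poolability model names no participant effect, so with positively correlated phase means its treatment-by-site test is too conservative and its averaged site test too liberal

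*SAP*

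**What the plan says.** SAP 5.2.1.2 and Protocol 10.4.2 give the same model. "The effect of investigational site will be evaluated using regression models, with primary endpoint as the dependent variable", and the terms are "treatment, investigational site, and the interaction term between treatment and investigational site as fixed effects". Neither section names a participant term or a phase term.

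The dependent variable exists once per phase: "The primary efficacy endpoint is derived by computing the mean of daily capture rate during each phase". SAP 5.2.2.2 builds the Draize endpoint in the same way. In this 2 by 2 crossover a completer therefore contributes two values, one per device.

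Where the plan specifies other mixed models, it names participant:

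- Capture-rate sensitivity models (SAP 5.2.2.1): "with treatment, phase, and study day as the fixed effect, and participant as the random effect".
- N-QoL model (SAP 5.2.3.1): "with treatment, phase, and day number as the fixed effect, and participant as the random effect".
- N-QoL model (Protocol 10.6.1): "with treatment and sequence as the fixed effect, and participant as the random effect".

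The number of sites is not settled. Protocol 4.1 says "Approximately 30 female participants from 2 sites will be enrolled into the study"; the synopsis says "Approximately 2 sites in France and approximately 2 sites in the U.S".

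**The concern.** Device varies within a woman and site varies between women, so the two effects need different error terms. A regression with fixed effects only has a single residual, which mixes within-woman and between-woman variance and treats about 60 records as independent. Protocol 6.7 justifies the crossover on the ground that comparing each woman with herself takes out between-woman variability, which presupposes positive correlation. The poolability model puts that variability back into the test of whether the device effect differs by site.

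No other model in the plan contains site. The pilot is meant to inform a later global trial, with sites in France and the U.S. As written, the model can miss a real site difference in device effect while reporting spurious differences in overall level.

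**Working it through.** **Inputs from the documents.** About 30 participants (SAP 2.4); 2 sites (Protocol 4.1) or about 4 (synopsis), so both are shown; 1:1 sequences in blocks of 2 stratified by site (SAP 2.3), so phase is nearly balanced over device within site.

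**Assumptions, because the documents give no values.** All 30 women complete both phases; splits 15/15 or 8/8/7/7; nominal 5% level; SD of a phase mean 15 points (capture-rate scale); r = 0.1, 0.3, 0.5, 0.7. The plan states no figure for this model, so there is none to reproduce.

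**Formulas.** With N women, S sites and complete pairs, the sums of squares separate:

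- treatment-by-site and within-woman error scale with SD²(1 − r);
- averaged site effect and between-woman error scale with SD²(1 + r);
- the model as written pools both errors on 2N − 2S degrees of freedom, with expectation SD².

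In large samples a nominal 5% test with k degrees of freedom and critical value c rejects a true null with probability P(χ²ₖ > c/(1 − r)) for the interaction and P(χ²ₖ > c/(1 + r)) for the averaged site effect. For 2 sites and r = 0.5, c = 3.84. The interaction rejects with P(χ²₁ > 7.68) = 0.6% and the site test with P(χ²₁ > 2.56) = 11%.

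**Small-sample results** (400,000 draws per setting from the corresponding chi-squares).

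| Quantity | r = 0.1 | 0.3 | 0.5 | 0.7 |
|---|---|---|---|---|
| Null interaction rejected, 4 sites | 3.5% | 1.3% | 0.3% | 0.0% |
| Null interaction rejected, 2 sites | 3.9% | 2.0% | 0.7% | 0.1% |
| Null averaged site effect rejected, 4 sites | 7% | 11% | 15% | 20% |
| Null averaged site effect rejected, 2 sites | 6% | 8.5% | 11% | 13% |

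**Interaction power**, as written vs within-woman differences, when one site's device effect deviates. The 4-site rows place the deviation at a site of 8 women.

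| Setting | r = 0.1 | 0.3 | 0.5 | 0.7 |
|---|---|---|---|---|
| 20 points, 4 sites | 41 vs 44% | 36 vs 55% | 31 vs 71% | 24 vs 92% |
| 20 points, 2 sites | 73 vs 75% | 75 vs 85% | 79 vs 94% | 84 vs 99.5% |
| 15 points, 4 sites | 23 vs 26% | 17 vs 33% | 12 vs 45% | 6 vs 68% |
| 15 points, 2 sites | 48 vs 50% | 47 vs 61% | 47 vs 75% | 46 vs 93% |

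With the 20-point deviation at a site of 7 women, the 4-site figures are 37/33/27/19% vs 41/51/67/89%.

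**95% CI half-width for one site's device difference**, using the expected error variance:

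- As written: t × 15 × √(2/n). For n = 7 (4 sites, 52 df): 2.007 × 15 × √(2/7) = 16.1 points. For n = 15 (2 sites, 56 df): 2.003 × 15 × √(2/15) = 11.0 points.
- Within-woman: t × 15 × √(2(1 − r)/n). For n = 7 (26 df, t = 2.056): 15.6/13.8/11.7/9.0 points across the four r values. For n = 15 (28 df, t = 2.048): 10.6/9.4/7.9/6.1 points.

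**Check of the correction.** In 20,000 record-level simulated trials per setting, participant blocks plus phase gave null interaction rejection of 4.9–5.4%, and the site test on within-woman means gave 5.0%. A separate simulation, which included unequal splits (12/8/6/4 and 20/4/4/2), gave 4.7–5.3% for both corrected tests at every r tried.

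**The case against.** The wording lists terms as fixed effects and does not say that nothing else enters, so a random participant effect is compatible with it; the defect could be called under-specification. That reading is weak, because the plan names participant in each of its other mixed models, and someone programming this section literally would fit ordinary regression.

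Other points stand and limit the finding:

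- Both directions need r > 0. A negative r reverses them (at r = −0.3 with 2 sites: site 1.9%, interaction 8.7%).
- The liberal result belongs to the site contrast averaged over devices. A site coefficient read within one reference device uses one record per woman and is not inflated in this way. The plan does not say which is meant.
- No alpha, decision rule or action on non-poolability is set, and SAP 5.2.1.3 makes P values exploratory.
- The SD and the deviations are assumed. In points, they describe capture rate and cannot describe Draize scores (0 to 4 per category, total 0 to 12). The null rejection rates do not depend on the SD.
- A random-effects fit with its variance bounded at zero is slightly off nominal at r = 0.1 with 4 sites (interaction about 5.3%, site about 4.0%), which is negligible beside the distortion removed.
- Near balance of phase within site means that adding phase matters less than adding participant.

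**Conclusion.** The point holds. As written, the poolability regression uses the wrong error term for data with two records per woman. For r between 0.3 and 0.7 it nearly disables the treatment-by-site test (null rejection 2.0% or less instead of 5%). It also raises the false-positive rate of the averaged site test to 8.5–13% with 2 sites or 11–20% with 4. At r = 0.1 the effect is minor. These figures rest on complete pairs, approximate normality and assumed r; the power and CI figures also rest on the assumed SD of 15.

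The harm is confined to the exploratory P values and CIs on site differences. The paired primary comparison and the sensitivity models that include participant are unaffected. It should be corrected, but it does not threaten the main result.

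**What to change.** In SAP 5.2.1.2 and Protocol 10.4.2:

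1. Add participant (nested in site) as a random effect and phase as a fixed effect, in line with the SAP's other mixed models. This also keeps women who have only one phase.
2. State which site test is meant: averaged over devices, or within one device.
3. Report the device difference for each site with its CI.
4. As an alternative for women with both phases, test the interaction on within-woman differences, with a sequence term to adjust for phase, and test site level on within-woman means. In simulation the sequence term changed power by at most 0.3 points.

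Separately, reconcile the number of sites between Protocol 4.1 and the synopsis.

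The cost is one clause in two places, one RANDOM statement and slightly more analysis work. No new data are needed.
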